Official Title	Pharmacy Delivery to Expand the Reach of PrEP in Kenya: Cluster-randomized Control Trial
NCT Number	NCT05842122
Document Type	Statistical Analysis Plan
Document Date	12/16/2025

Pharmacy delivery to expand the reach of PrEP in Kenya: cluster-randomized control trial

Pharm PrEP cRCT

Statistical Analysis Plan

Version 1.9

16 December 2025

NCT05842122

Based on protocol version 2.2 dated 23 July 2025

FINAL

[name]

Contents

Introduction	4
1. Study Objectives and Overview	4
2. Study Population	5
3. Study Outcomes	6
4 Study Design	9
4.2 Trial	9
4.3 Intervention	10
4.4 Randomization	10
4.5 Sample size and power	11
5 Planned Analyses	14
6 General Statistical Considerations	14
6.2 Data sources	14
6.3 Descriptive statistics	17
6.4 Statistical testing and models	17
6.5 Exposure groups	17
6.6 Analysis populations	17
6.7 Missing values	18
7 Data Analysis	18
7.2 Study enrollment	18
7.3 Pharmacy characteristics	18
7.4 Characteristics at enrollment	18
7.5 Outcomes	18
7.6 Safety	22
7.6.1 HIV seroconversion	22
7.7 Post-unblinding update: December 16, 2025	23

Introduction

This statistical analysis plan (SAP) describes the statistical procedures and analyses and data displays that address study objectives specified in protocol version 1.1 of the Pharm PrEP cRCT (a study of pharmacy-delivered PrEP/PEP in Kenya).

New versions of the SAP will be issued to document updates and changes in the plan. Any meaningful changes or additions to this SAP (e.g., in response to protocol amendments or violations of assumptions underlying pre-planned analyses), and the timing of such changes in relation to timing of performing the analysis will be documented in the SAP.

1. Study Objectives and Overview

Protocol title	Pharmacy delivery to expand the reach of PrEP in Kenya: cluster-randomized control trial
Short title	Pharm PrEP cRCT
Design	Cluster-randomized controlled trial
Study exposures	Each pharmacy is randomized to either provision of PrEP/PEP in pharmacies either provided by a pharmacist for free (Arm 1), for a fee (Arm 2), or by an HTS counselor for free (Arm 3); or referral to a clinic for PrEP/PEP (Arm 4, standard of care)
Population	Pharmacies must be registered; pharmacists must be licensed and HTS counselors must be certified; enrolled clients must be adults (≥ 16 years old), at risk of HIV, and eligible for PrEP/PEP (according to the prescribing checklist)
Study size	At least 1,119 PrEP initiations and 2,400 PEP initiations for the cluster-randomized control trial
Study follow-up	At least 20 months for accrual (until sample size achieved) plus follow-up of up to 270 days.
Study sites	60 private pharmacies in Kenya (Nairobi; Kiambu; Kisumu/Siaya; and Homa Bay/Migori).
Objective	Quantify the effect of three models of pharmacy-delivered PrEP/PEP (sustained by clients; sustained by implementors; and sustained by implementors with support from HTS counselors) compared to pharmacy referral to clinic-based PrEP/PEP services (SOC) on PrEP/PEP outcomes and implementation outcomes
Outcomes	Primary: 
• PrEP initiation within 60 days of enrollment;• PrEP continuation (i.e., one refill) by 60 days

Secondary:

- PrEP initiation within 270 days;
- Any PrEP continuation within 270 days;
- At least 2 PrEP refills within 270 days;
- Any stopping and restarting PrEP (i.e., PrEP reinitiation);
- PEP initiation within 60 and 270 days;
- PEP-to-PrEP transition by 60 and 270 days;
- PrEP-to-PEP transition by 60 and 270 days;
- Recurrent PEP use by 60 and 270 days;
- PrEP adherence at 60 days;
- PrEP/PEP initiation within 60 and 270 days;
- Any PrEP/PEP continuation by 60 and 270 days

Tertiary:

- Follow-up HIV testing by 60 and 270 days;
- Behaviors associated with HIV risk at 60 and 270 days;
- PrEP coverage (exploratory)
- Acceptability; quality of care perceptions; willingness to pay; fidelity (client outcomes); acceptability; feasibility; adaptations; perceived self-efficacy; willingness to charge (provider/counselor outcomes); sustainability (pharmacy outcome)

2. Study Population

Adults at risk of HIV acquisition (determined by screening tools, self-report, and provider assessment) and eligible for pharmacy-delivered PrEP/PEP services (i.e., no medical conditions that might contraindicate PrEP/PEP safety) identified by screening at one of 60 participating pharmacies in Kenya whose data (pharmacy/clinic records, survey, and/or interview) were collected.

Pharmacies

Eligibility criteria:

- Registered with the Kenya Pharmacy and Poisons Board (PPB)
- Premises must comply with the requirements of the Pharmaceutical Society of Kenya and the Kenya Pharmaceutical Association
- Must have ≥1 full-time licensed pharmacist or pharmaceutical technologist on staff
- Must have a private room where HIV testing and PrEP/PEP counseling can occur

- Must be willing to use a study-specific module within a digital platform (Maisha Meds) to record pharmacy PrEP/PEP dispensing
- Owner must agree to allow a trained research assistant to come to the pharmacy on select days to collect data from a random subset of participants
- Owner must agree to allow providers to participate in a monitored WhatsApp group, optional surveys, and in-depth interview (IDI)
- Owner must agree to allow providers to routinely engage with a technical assistant

Pharmacists/HTS counselors

Eligibility criteria:

- ≥ 18 years old
- Licensed pharmacist, licensed pharmaceutical technologist, or NASCOP-certified HTS counselor
- Willing to provide PrEP and PEP services, including HIV testing and associated counseling services
- Completed training on PEP/PrEP service delivery at pharmacies, including certification for rapid diagnostic testing
- Able and willing to provide consent
- Complete study training
- Willing to use a study-specific module within a digital platform (Maisha Meds) to document PrEP/PEP services rendered

Clients

Inclusion criteria:

- ≥ 16 years old, including emancipated minors 16-17 years old
- Interested in initiating PrEP or PEP
- Meets all criteria for PrEP or PEP initiation on the Prescribing Checklist, including being at risk for HIV and not having any medical conditions that might contraindicate PrEP/PEP safety
- Able and willing to provide informed consent

Exclusion criteria:

- Unwilling to provide a phone number at which an RA can reach them for completing surveys and communicating important study-related information
- Currently enrolled in any other HIV vaccine or prevention trial
- Having a condition that would preclude provision of informed consent, make study participation unsafe, complicate interpretation of outcome data, or otherwise interfere with achieving study objectives

3. Study Outcomes

Planned primary outcomes are PrEP initiation and PrEP continuation. These outcomes will be defined as follows:

- PrEP initiation: the number of participants at each pharmacy that initiated (i.e., were dispensed) PrEP at the pharmacy or clinic **within 60 days** of initial pharmacy-based screening. *Comparisons between intervention arms and the control will rely on self-*

report from the 60-day client survey, while comparisons between intervention arms will employ pharmacy records.

- PrEP continuation: the number of participants at each pharmacy that initiated PrEP at the pharmacy or clinic and returned to the pharmacy or clinic and refilled PrEP **within 60 days** of initial pharmacy-based screening. *Comparisons between intervention arms and the control will rely on self-report from the 60-day client survey, while comparisons between intervention arms will employ pharmacy records.*

Secondary outcomes include those related to PrEP initiation, PrEP continuation, PrEP adherence, PEP initiation, PEP-to-PrEP transition, and repeat PEP use.

- PrEP initiation: the number of participants at each pharmacy that initiated (i.e., were dispensed) PrEP at the pharmacy or clinic **within 270 days** of initial pharmacy-based screening
- PrEP continuation:
 - The number of participants at each pharmacy that initiated PrEP at the pharmacy or clinic and returned to the pharmacy or clinic and refilled PrEP **within 270 days** of initial pharmacy-based screening (regardless of any gaps in pill coverage).
 - The number of participants at each pharmacy that initiated PrEP at the pharmacy or clinic and **refilled PrEP at least twice within 270 days** of initial pharmacy-based screening (regardless of any gaps in pill coverage).
 - The number of participants at each pharmacy that initiated PrEP at the pharmacy or clinic and refilled PrEP more than 7 days after their expected refill date (i.e., stopping and restarting, also referred to as “PrEP reinitiation”) **within 270 days** of initial pharmacy-based screening.
- PrEP adherence: The median adherence score (0-100) among participants at each pharmacy who initiated PrEP at the pharmacy or clinic –using the Wilson et al. scale (2020, *AIDS*)—as measured at **60 days** following initial pharmacy screening.
- PEP initiation: the number of participants at each pharmacy that initiated (i.e., were dispensed) PEP ≥ 1 times at the pharmacy or clinic within 3 days, as measured at **60 days** and **270 days** following initial pharmacy screening.
- PEP-to-PrEP transition: the number of participants at each pharmacy that successfully completed PEP (tested negative or self-reported testing negative for HIV between 28 and 45 days after initiating PEP at the pharmacy) **and** initiated PrEP at the pharmacy or clinic as measured at **60 days** and **270 days** following initial pharmacy screening.
- PrEP-to-PEP transition: the number of participants at each pharmacy that initiated (i.e. were dispensed) PrEP and subsequently initiated PEP at the pharmacy or clinic within 3 days, as measured at **60 days** and **270 days** following initial pharmacy screening.
- PEP/PrEP initiation: the number of participants at each pharmacy that initiated (i.e., were dispensed) either PEP or PrEP at the pharmacy or clinic (within 3 days for PEP clients) as measured at **60 days** and **270 days** following initial pharmacy screening.
- PEP/PrEP continuation: the number of participants at each pharmacy that (1) initiated PrEP and refilled PrEP or later were dispensed PEP; or (2) initiated PEP and transitioned to PrEP or later were dispensed PEP again as measured at **60 days** and **270 days** of initial pharmacy screening.

- Recurrent PEP use: the number of participants at each pharmacy that were dispensed PEP ≥ 2 times as measured at **60 days** and **270 days** of initial pharmacy screening.

Tertiary outcomes include related behaviors as well as implementation outcomes based on a variety of scales:

- Follow-up HIV testing: the number of participants at each pharmacy engaging in HIV testing following the pharmacy PrEP/PEP visit (not including the initiation visit), as measured at **60 days** and **270 days** following initial pharmacy screening.
- HIV risk: the number of participants engaging in specific self-reported behaviors associated with HIV risk reported in the time frame following pharmacy PrEP or PEP delivery, such as any condomless sex in the past month and self-reported perception of HIV risk acquisition in the present and future.
- PrEP coverage (exploratory): duration of time on PrEP based on dates of dispensing and the quantity of pills dispensed at each visit using all longitudinal data available at completion of the cRCT.
- Client implementation outcomes
 - Acceptability: assessed in the extended client survey at different time points over the trial duration using questions that measure different domains of the Theoretical Framework of Acceptability (Sekhon et al., 2017, *BMC Health Serv Res*), which consists of seven component constructs (e.g., affective attitude, burden, perceived effectiveness).
 - Fidelity: the number and proportion of participants that received different core components of the intervention (e.g., counseling on HIV risk, medical history, HIV testing, drug dispensing) as specified in the protocol. Assessed in the extensive client survey at different time points over the trial duration.
 - Willingness to pay: the amount eligible pharmacy PrEP clients are willing to pay for each pharmacy PrEP or PEP visit, as assessed in the extensive client survey at different points in time over the trial duration.
 - Quality of care perceptions: assessed in the extensive client survey at different time points over the trial duration using a modified perceived service quality scale (pSQ-SF6) (Carter et al., 2022, *Res Social Adm Pharm*), with higher score indicating higher perceived service quality.
- Provider/counselor implementation outcomes
 - Acceptability: assessed in the provider survey at different time points over the trial duration using questions that measure different domains of the Theoretical Framework of Acceptability (Sekhon et al., 2017, *BMC Health Serv Res*), which consists of seven component constructs (e.g., affective attitude, burden, perceived effectiveness).

- Feasibility: assessed in the provider survey at different time points over the trial duration using questions based on the Feasibility of Intervention Measure (FIM) (Weiner et al., 2017, *Implement Sci*).
- Perceived self-efficacy: assessed in the provider survey at different time points over the trial duration using statements that assess providers' level of confidence delivering different core components of the pharmacy PrEP intervention (e.g., counseling, HIV testing, referral, etc.).
- Willingness to charge: the amount pharmacy providers are willing to charge for each pharmacy PrEP or PEP visit under different scenarios. Assessed in the provider survey at different time points over trial implementation.
- Pharmacy implementation outcomes
 - Sustainability: comparison of study outcomes during the first half and second half of implementation.
 - Adaptations: measured in the technical assistance reports using the Framework for Reporting Adaptations and Modifications to Evidence-based Implementation Strategies (FRAME-IS) (Miller et al., 2021, *Implement Sci*).

[figure not shown]
4 Study Design

The study is a cluster-randomized control trial (cRCT). The intervention will be introduced in a parallel fashion with a brief ramp-up period (i.e., staggered launch).

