4.5 Sample size and power

We had planned to analyze the PrEP and PEP initiation and continuation outcomes as binary outcomes, using an individual-level analysis. However, in September 2023, it became apparent that the denominators that would be used in these estimates (number enrolled) would vary greatly across arms (and indeed would be affected by which arm a pharmacy was randomized to) and would likely lead to biased estimates of the proportions initiating/continuing in each arm. In particular, the intervention is thought to (a) have an effect on likelihood of enrollment and (b) have an effect on likelihood of PrEP/PEP initiation (and thus continuation); we would like to capture the total effect of the intervention, i.e., both (a) and (b). However, by only considering individuals who were enrolled (which corresponds to the previous analytic approach), we would only capture (b), and would be ignoring (a).

Thus, we are instead pursuing a cluster-level analysis of the initiation and continuation outcomes, where each cluster (pharmacy) is summarized by the number of initiations/continuations over the course of the study, accounting for pharmacy size (i.e., pharmacy flow). This is reflected in the analytic approach described below.

The anticipated number of PrEP and PEP initiations and continuations within 60 days of pharmacy screening per pharmacy in each study arm over 16 months of implementation are given in **Table 2**. Estimates of the total counts per pharmacy in each arm were based on those observed in pilot studies of pharmacy-delivered PrEP and PEP services: (1) one which offered PrEP for a fee of 350 KES in 4 pharmacies—informing Arm 1 PrEP initiation and continuation estimates (Ortblad et al., J Int AIDS Soc. 2023), and (2) another which offered PrEP and PEP services for free in 12 pharmacies—informing Arm 2 PrEP initiation and continuations estimates, as well as PEP initiation and continuation estimates (Roche et al., CROI 2023). The estimates in other arms were based on the hypothesized difference between the arms—with the hypothesis that Arm 3 (implementor-sustained with HTS counselor support) would perform best, followed by Arm 2 (implementor-sustained), Arm 1 (clients-sustained), and Arm 4 (SOC referral). The PrEP continuation estimates in Arm 4 (SOC referral) were additionally informed by the Partners Scale-up Project, with delivered PrEP services in 24 public clinics in Kenya. Based

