In particular, to estimate power, it was assumed that the average pharmacy flow was the same across the four arms; there is no a priori reason to assume otherwise. We further assumed a coefficient of variation (CV) of 0.25. The coefficient of variation characterizes the variability in number of PrEP initiations (relative to pharmacy size) across pharmacies. While this is difficult to know ahead of time, it is typically <0.25 (Hayes and Bennett, *IJE*, 1999). A CV of 0.25 would roughly correspond to a situation where, for example, the average number of PrEP initiations was 20/pharmacy, and 95% of pharmacies had between 10 and 30 initiations (assuming equal flow across pharmacies); this seems to be a reasonable degree of variability in our setting. Given that the analyses will include comparisons of Arms 1, 2, and 3 vs. 4, we used a Bonferroni correction to our alpha level (two-sided alpha = 0.05/3) for the PrEP 60-day initiation/continuation outcomes and the combined PrEP/PEP outcomes (primary and key secondary outcomes).

Based on the hypothesized number of PrEP/PEP initiations and continuations in **Table 3**, we estimated the power would be very high for comparing Arms 2 and 3 to Arm 4 for PrEP initiation

and continuation (primary outcomes) and the combined PrEP/PEP initiation and continuation outcomes (key secondary outcomes; **Table 4**). For the Arm 1 vs. Arm 4 comparisons, the power is estimated to be 80% for PrEP initiation (as designed), 100% for the combined PrEP/PEP initiation outcome, and lower for the continuation outcomes.

→ **Primary outcome assessment will be completed after a total of 1,119 PrEP initiations are achieved. A study duration of 20 months of implementation is targeted.**

Table 3: Number of PrEP, PEP, and PrEP/PEP initiations and continuations per pharmacy (k=15/arm, k=60 total) for >80% power in our PrEP outcomes of interest

	1: Client-sustained	2: Implementor-sustained	3: HTS supported	4: Referral (SOC)	TOTAL (across 60 pharms)
PrEP initiations	16.13	22.18	26.21	10.08	1,119
PEP initiations	32	48	64	16	2,400
Total PrEP/PEP initiations	48.13	70.18	90.21	26.08	3,519
PrEP continuations	8.06 (50% of initiations)	15.52 (70% of initiations)	20.97 (80% of initiations)	6.05 (60% of initiations)	759
PEP continuations	4.34 (13.6% of initiations)	9.12 (19.0% of initiations)	13.90 (21.7% of initiations)	2.61 (16.3% of initiations)	450

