We will estimate the ratio of PrEP initiation rates (number of initiations per clients served at the pharmacy, accounting for pharmacy volume over the implementation period) comparing each intervention arm to the SOC arm using a Poisson generalized linear model with log link and robust standard errors. The model will allow for overdispersion to account for increased variability in rates. The outcome will be number of self-reported PrEP initiations from the 60-day brief client survey in each pharmacy. A cluster-level analysis was chosen for the outcome of PrEP initiation because the number of individuals enrolling in the study at a given pharmacy was found to be heavily dependent upon the study arm of the pharmacy. Thus, the available denominator for the individual-level PrEP initiation outcome, number of individuals enrolled in the study, was a poor proxy for the quantity of interest, number of pharmacy PrEP candidates (i.e., individuals determined at risk of HIV acquisition who meet the pharmacy PrEP prescribing checklist criteria). Instead, we will pursue a cluster-level analysis where the outcome is number of initiations at each pharmacy and we account for pharmacy volume as a way to make fair comparisons across pharmacies.

The model will include study arm as a four-level categorical (nominal) variable and a continuous offset variable reflecting pharmacy volume (number of clients per unit time). Pharmacy volume will be measured as the number of transactions per month. Estimates of monthly volume will be obtained up to three times in each pharmacy during the course of the study (to account for seasonal variations); missing observations will be imputed, and we will take the average of the three assessments. To account for the stratified randomization procedure, we will adjust for county as a categorical (nominal) variable. As noted in Section 6.7, our missing imputation strategy (i.e., imputing missing outcome data as failures) will not affect the primary analysis of the pharmacy-level count data and will only influence the secondary analysis described in Section 7.5.1.3.

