7.5.1.3 Secondary Analyses

For the outcome of PrEP continuation at 60 days, we will conduct a **secondary analysis** of the proportion of participants continuing PrEP at 60 days among those who initiated PrEP. In particular, we will estimate the risk difference of PrEP continuation between each intervention arm and the SOC arm using a Poisson generalized estimating equations (GEE) model with identity link and robust standard errors (Pedoza and Truong, BMC Med Res Methodology, 2016). The outcome will be self-reported PrEP continuation from the brief client survey. The model will include study arm as a four-level categorical (nominal) variable and adjust for county to account for the stratified randomization procedure. To account for varying cluster size (number of PrEP initiators), we will use an independent working correlation matrix and weights for cluster size (Wang et al., Contemp Clin Trials, 2022). Missingness will be addressed as described in Section 6.7. In the event that this model does not converge or yields invalid estimates (e.g., risk differences or confidence intervals outside of ± 1), we will instead fit a modified Poisson GEE model—i.e., a GEE with log link and robust standard errors (Yelland et al., AJE, 2011)—to estimate the relative risk comparing each intervention arm to the SOC arm. Importantly, as this analysis is restricted to those who have initiated PrEP, randomization is not maintained. Thus, we would need to adjust for factors related to initiation in order to remove the bias incurred by selecting only those who initiate (Hernan and Hernandez-Diaz, Clin Trials, 2012).

Additionally, **secondary analyses** for PrEP initiation and continuation at 60 days will be conducted to evaluate whether the effect of the intervention differs by urban/rural pharmacy status, location in Western vs. Eastern Kenya, or by the proportion of enrolled individuals who (1) are female or (2) over the age of 25. This will be done by adding two terms to the model described in Section 7.5.1.1: the main effect of the subgroup variable (e.g., percent female) and an interaction between the categorical intervention variable and the subgroup variable. As part of this analysis, we will estimate the intervention effects within each subgroup.

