7.5.2 Secondary and tertiary outcomes

The analysis of the secondary outcomes of PrEP initiation within 270 days, any PrEP continuation within 270 days, at least 2 PrEP refills, any stopping and restarting PrEP, PEP initiation, PEP-to-PrEP transition, recurrent PEP use, PrEP/PEP initiation, PrEP/PEP continuation, PrEP adherence and the tertiary outcome of follow-up HIV testing will be similar to those described in Sections 7.5.1.1. Furthermore, the secondary analyses proposed in Section 7.5.1.3 will be performed for these outcomes (as appropriate for the outcome), with the exception of the secondary analysis investigating interactions. For the analysis of PrEP initiation with 270 days, the sensitivity analysis described in Section 6.7, in which PrEP initiation at 60 days is used to impute missing PrEP initiation at 270 days, will be performed.

For the exploratory outcome of PrEP coverage, descriptive statistics in each arm will be provided.

The tertiary outcomes (including acceptability, appropriateness, willingness to pay/charge, feasibility, and adaptations) will be summarized using descriptive statistics when assessed quantitatively and analyzed using a combination of inductive and deductive approaches (e.g., thematic content analysis) when assessed qualitatively. Similarly, the HIV risk behavior outcomes will be analyzed descriptively. No formal statistical comparisons will be performed for these tertiary outcomes.

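### The main PrEP adherence comparison is restricted to clients who initiated PrEP, but it is analysed as a randomised contrast without the adjustment the SAP requires for another initiator-only analysis

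*SAP*

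**What the plan says.** **Outcome.** Section 3 lists PrEP adherence at 60 days as a secondary outcome: "The median adherence score (0-100) among participants at each pharmacy who initiated PrEP at the pharmacy or clinic". Each pharmacy contributes one number, computed only from clients who started PrEP. Table 5 gives the source as self-report in the brief client survey.

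**Main analysis.** Section 7.5.2 states that the analysis of a list of outcomes ending in "PrEP adherence and the tertiary outcome of follow-up HIV testing will be similar to those described in Sections 7.5.1.1". Section 7.5.1.1 estimates an effect by "comparing each intervention arm to the SOC arm using a Poisson generalized linear model with log link and robust standard errors", with arm, county and a pharmacy-volume offset. Adherence is not among the outcomes given the 0.0167 threshold in Section 6.4, so the general two-sided 0.05 rule applies.

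**Secondary analyses.** Section 7.5.2 adds that "the secondary analyses proposed in Section 7.5.1.3 will be performed for these outcomes (as appropriate for the outcome").

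**What the SAP says about selection.** Section 4.5 gives the reason for moving the initiation and continuation outcomes to pharmacy counts: "the intervention is thought to (a) have an effect on likelihood of enrollment and (b) have an effect on likelihood of PrEP/PEP initiation". Section 7.5.1.1 reports that enrolment numbers were found to depend heavily on arm. Section 7.5.1.3, on the proportion continuing among initiators, warns that "as this analysis is restricted to those who have initiated PrEP, randomization is not maintained" and says that factors related to initiation would have to be adjusted for.

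**The concern.** Randomising pharmacies protects a comparison of everything that happens at a pharmacy. It does not protect a comparison of a subgroup that forms after randomisation and in response to it. The count outcomes avoid this problem because they set events against pharmacy volume. A median among initiators cannot avoid it, since clients who did not start PrEP have no score.

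The SAP recognises this for the continuation proportion and prescribes adjustment. Adherence carries the same restriction, yet its main analysis has neither the adjustment nor the warning. The question is separate from whether a Poisson count model suits a 0-100 score: a linear model without the offset would have the same selection problem.

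At stake is how an adherence difference at p < 0.05 would be read. It could be reported as an effect of pharmacy delivery on pill-taking when it reflects, in whole or in part, different people starting PrEP.

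**Working it through.** **1. Check the counts.** The SAP states no power or effect size for adherence, so the only planned figures to build on are the Table 3 initiation counts. To confirm that they are the design's working values, I reproduced Table 4 with the cluster-rate formula:

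power = Φ( √[ (c − 1)(m1 − m0)² / { (m0 + m1) + CV²(m0² + m1²) } ] − z(1 − α/2) )

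The inputs are c = 15 pharmacies per arm (Section 4.2), CV = 0.25 and α = 0.05/3 (Section 4.5).

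For PrEP initiations, Arm 1 v Arm 4, m1 = 16.13 and m0 = 10.08:
- numerator: 14 × 6.05² = 512.4
- denominator: 26.21 + 0.0625 × (16.13² + 10.08²) = 48.82
- power: 80.1% (Table 4: 80%)

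The same formula gives 23.2% for PrEP continuations (Table 4: 23%) and 48.4% for combined continuations (Table 4: 48%). The total also agrees: 15 × (16.13 + 22.18 + 26.21 + 10.08) = 1,119.

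**2. How far the initiator groups differ in size.** Table 3 gives PrEP initiations per pharmacy in Arms 1, 2, 3 and 4 as "16.13 22.18 26.21 10.08".

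| | Arm 1 | Arm 2 | Arm 3 |
|---|---|---|---|
| Ratio to Arm 4 | 16.13/10.08 = 1.60 | 22.18/10.08 = 2.20 | 26.21/10.08 = 2.60 |
| Share beyond the Arm 4 number | 1 − 10.08/16.13 = 37.5% | 1 − 10.08/22.18 = 54.6% | 1 − 10.08/26.21 = 61.5% |

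The second row can be read as the share with no Arm 4 counterpart only under an assumption that the SAP does not state: everyone who would start under referral would also start in the pharmacy arm.

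**3. What a difference in make-up would do.** Suppose no client's adherence is changed by the arm, and the additional initiators differ from the others by d points on average. The expected difference in mean score against Arm 4 is then share × d. The SAP does not give d, so a range is shown. The sign of the result is the sign of d.

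| Assumed size of d | Arm 1 | Arm 2 | Arm 3 |
|---|---|---|---|
| 5 points | 1.9 | 2.7 | 3.1 |
| 10 points | 3.8 | 5.5 | 6.2 |
| 20 points | 7.5 | 10.9 | 12.3 |

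These are differences in means. A difference in pharmacy medians would be similar but not identical.

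**4. Does any other provision cover it?** The extension of Section 7.5.1.3 is qualified as where appropriate, names no covariates for adherence, and adds a secondary analysis. The Section 7.5.1.1 contrast remains the main one. Section 7.4 tabulates the characteristics of initiators by arm, which is descriptive only.

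**The case against.** **The SAP may already plan the remedy.** The list in Section 7.5.2 names adherence, the Section 7.5.1.3 analyses are carried over to it, and an initiator-only outcome is the most natural place for that adjustment. This stands in part: the authors know the problem, and the adjusted analysis may be intended. But on the wording it would be secondary and its covariates are not fixed, so the headline contrast stays unadjusted.

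**The direction cannot be claimed.** A reader might infer that pharmacy arms recruit less motivated clients, so that the bias runs against them and most of all against Arm 3. The documents do not support this. They establish that numbers depend on arm, not that the additional initiators adhere less. Table 3 expects continuation among initiators of 70% in Arm 2 and 80% in Arm 3, against 60% in Arm 4. Those figures mix model effect with make-up, so they do not exclude selection, but they lend no support to that reading. The estimates for Arm 1, the client-sustained arm, come from a pilot that charged a fee, and a fee could select more motivated clients.

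**The false-positive rate cannot be claimed either.** A reader might want one figure. With an assumed base score of 75, person SD of 25, between-pharmacy SD of 5 and additional initiators 10 points lower, a t test on pharmacy medians rejects in about 15%, 28% and 38% of simulated trials for Arms 1, 2 and 3. With the named Poisson model, a volume offset (assumed volume CV 0.25) and the same 10-point gap, rejection is only about 9% to 18% across arms, against 6% to 8% with no gap. The rates depend on inputs and a model choice that the SAP does not settle, so none is put forward as the size of the problem.

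**The stakes are limited.** Adherence is neither a primary nor a key secondary outcome, and the primary counts are untouched. This stands.

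**Conclusion.** The inconsistency is in the text. An initiator-only outcome has as its main analysis a formal arm-versus-SOC comparison adjusted only for county, while the same SAP says that such a restriction breaks randomisation and calls for adjustment. The adherence contrast can therefore combine an effect on pill-taking with a difference in who initiated.

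The direction is unknown. The size is 0.375d, 0.546d and 0.615d points for Arms 1, 2 and 3. This rests on the planned Table 3 counts (themselves scaled to give 80% power for one comparison), on the assumption that referral initiators are a subset of those who would start in a pharmacy arm, and on a d that the SAP does not provide. A bias of either sign would make a p < 0.05 result unreadable as an effect of the pharmacy model.

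The point is worth correcting because the change is cheap, but it concerns one secondary outcome and does not affect the primary conclusions.

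**What to change.** In Section 7.5.2:

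1. Take PrEP adherence out of the outcomes analysed as in Section 7.5.1.1.
2. State that its main arm-versus-SOC analysis is an individual-level model among PrEP initiators, clustered by pharmacy, with arm, county and named enrolment characteristics related to initiation. Items already collected would serve: age, sex, marital or relationship status and HIV risk behaviours.
3. Report an estimate and confidence interval, labelled as conditional on initiation and not protected by randomisation, with no significance claim at 0.05.
4. Keep the currently specified Section 7.5.1.1 analysis as a reported supplementary result. Log the change as made after unblinding: Section 7.7 dates unblinding to 6 November 2025, and the Introduction provides for documenting the timing of changes.

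A count of clients still taking PrEP at 60 days, with the volume offset, is optional. The primary continuation count already gives most of that all-comer comparison. The survey item covers PrEP and PEP together and measures persistence rather than adherence. Like any survey-based count, it is exposed to the arm-dependent survey completion described in Section 7.7.

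**Cost.** SAP wording and one further model; no new data or participants. The downside is that adjustment covers only measured characteristics, so some selection bias may remain, including any from motivation or from who answered the survey. The label in step 3 is there for that reason.
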